## 3.2 Study Outcome Measures

### 3.2.1 Primary Outcome Measures:

The efficacy of azithromycin versus placebo on Day 5 will be based on clinical improvement.

- Clinical improvement will be defined as fulfillment of **all** the following criteria:
  1. Improvement in at least two symptoms present at enrollment (i.e., cough, sputum production, chest pain, or difficulty breathing) or one symptom and at least one vital sign abnormality present at enrollment. For symptoms, at least a one-step improvement (e.g., improvement from moderate to mild cough) will be considered a clinical improvement (Table 1). For vital sign abnormalities, normalization of the

presenting abnormal vital sign will be considered a clinical improvement. Qualifying vital signs and their normal values will include the following:

- temperature (<37.8°C or 100.0°F),
  - pulse (<90 bpm),
  - respiratory rate (≤20 breaths per minute),
2. Absence of deterioration in any qualifying symptom (i.e., cough, sputum production, chest pain, or difficulty breathing); or new vital sign abnormality not present at enrollment. For symptoms, at least a one-step deterioration (e.g. worsening from mild to moderate cough) will be considered clinical deterioration (Table 1).
  3. Absence of fever in the day preceding or at the Day 5 Visit (fever is defined as ≥37.8 °C or 100.0 °F, measured anywhere on the body).
  4. No medically attended visit to an ambulatory medical facility (e.g., ED, outpatient clinic, urgent care center) or hospitalization for persistent or worsening LRTI at any time after randomization (persistent or worsening LRTI is defined as receipt of a non-study antibiotic [parenteral or oral] treatment for LRTI or its complication).  
**Note:** receipt of a non-study antibiotic after study Day 5 will not be regarded as satisfying this definition if it is related to a new non-respiratory process that is unrelated to the prior diagnosis of LRTI

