### 9.5.2 Individual Halting Rules (Termination of Study Product Administration)

Study product administration may be discontinued if any of the following criteria are met:

- Any clinical adverse event (AE), intercurrent illness, or other medical condition occurs that, in the opinion of the investigator, continued receipt of study product would not be in the best interest of the subject;
- New onset of illness or condition that meets exclusion criteria, at the investigator's discretion
- Inadequate clinical response that requires off-study antimicrobial therapy.
  - Subjects who require off-study antimicrobial therapy will be defined as having an inadequate clinical response.

Subjects may stop study drug treatment at any time of their own volition or at the advice of their treating provider or the study investigators. Subjects who stop study product for any reason will be regarded as having withdrawn from treatment but not as having withdrawn from the study (i.e, subjects will be asked to continue to participate in follow-up visits). All subjects with an inadequate clinical response will be referred to a non-study healthcare provider for evaluation and possible treatment outside of the clinical study. If requested, unblinding can occur if clinically indicated as determined by the treating clinician and the study's site investigator.

At the time of withdrawal, subjects will undergo an early termination visit if they are not willing to participate in the remaining follow-up visits.

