## **11.4 Final Analysis Plan**

The intention-to-treat (ITT) analysis population will consist of all randomized subjects. According-to-protocol (ATP) analysis populations will consist of subjects with no major protocol deviations regarding inclusion/exclusion criteria that consumed 5 doses of study product by Visit 3. The first dose of study drug should be taken within 24 hours of randomization. Subjects who miss a scheduled dose but resume the recommended dosing schedule within 24 hours remain eligible for ATP. However, in order for a subject to be eligible for the ATP-5 analysis, Visit 3 should be performed on or after the last day of study drug consumption while remaining within the 5+3 window. The ATP-5 analysis population will have the further restriction that the subjects must have completed an in-person Visit 3 within the protocol-defined time window. The ATP-11 analysis population will consist of the ATP analysis population with the further restriction that the subjects must have completed Visit 4 within the protocol-defined time window. The ATP-28

analysis population will consist of the ATP analysis population with the further restriction that the subjects must have completed Visit 5 within the protocol-defined time window.

Unless otherwise stated, all hypothesis tests and confidence intervals will be two-sided with  $\alpha=0.05$ . Statistical tests and confidence intervals will not correct for multiplicity.

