#### **11.4.2 Secondary Analyses**

1. The non-inferiority analysis of placebo versus azithromycin with respect to clinical improvement at Visit 3 (as defined in Section 3.2.1), using a non-inferiority margin of 12.5%, will be repeated as described in Section 11.4.1 using the ATP-5 analysis population.
2. The non-inferiority analysis of placebo versus azithromycin with respect to clinical improvement at Visit 4 (as defined in Section 3.2.1), using a non-inferiority margin of 12.5%, will be repeated as described in Section 11.4.1 using the ITT analyses population as well as ATP-11 analysis population.
3. The non-inferiority analysis of placebo versus azithromycin with respect to clinical improvement at Visit 5 (as defined in Section 3.2.1), using a non-inferiority margin of 12.5%, will be repeated as described in Section 11.4.1 using the ITT analyses population as well as ATP-28 analysis population.
4. Using the ATP-11 and ATP-28 analysis populations, respectively, the mean number of days of antibiotic use from Day 1 until Visit 4 or Visit 5 will be computed for placebo versus azithromycin, in addition to an estimated difference in means and associated 95% confidence intervals. The significance of the difference in means will be tested by a t-test.
5. Using the ATP-11 and ATP-28 analysis populations, respectively, the proportion of subjects with one or more return visits to a physician's office or urgent care for persistent or worsening LRTI at any time after randomization by Visit 4 or by Visit 5 will be

computed for placebo versus azithromycin, in addition to an estimated odds ratio and associated 95% confidence intervals. The significance of the difference in proportions will be tested by a Fisher's Exact Test.

6. Using the ATP-11 and ATP-28 analysis populations, respectively, the proportion of subjects with one or more emergency department visits for persistent or worsening LRTI at any time after randomization by Visit 4 or by Visit 5 will be computed for placebo versus azithromycin, in addition to an estimated odds ratio and associated 95% confidence intervals. The significance of the difference in proportions will be tested by a Fisher's Exact Test.

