7. Using the subsets of the ATP-11 and ATP-28 analysis populations, respectively, consisting of subjects not hospitalized at the enrollment and randomization visit, the proportion of subjects with one or more hospitalizations for persistent or worsening LRTI at any time after randomization by Visit 4 or by Visit 5 will be computed for placebo versus azithromycin, in addition to an estimated odds ratio and associated 95% confidence intervals. The significance of the difference in risk will be tested by a Fisher's Exact Test.
8. Using the ATP-11 and ATP-28 analysis populations, respectively, the proportions of subjects exhibiting improvement in at least one presenting symptom (Table 1) by Visit 4 or by Visit 5 will be computed for placebo versus azithromycin, in addition to an estimated odds ratio and associated 95% confidence intervals. The significance of the difference in proportions will be tested by a Fisher's Exact Test. The analysis will be repeated, analyzing each symptom individually.
9. The Day 5 DOORs (an ordinal outcome defined in Section 3.2.3) will be compared between the placebo and azithromycin arms. The sum of the probability that a randomly selected subject will have a better DOOR if assigned to the placebo arm plus one-half the probability of equal DOORs will be estimated. The null hypothesis to be tested is that the probability is equal to 0.50 (lack of superiority of azithromycin therapy). The analysis will be carried out using the ITT analysis population, with missing DOOR values (treated as continuous) imputed using multiple imputation, utilizing linear regression models. The analysis will be repeated using the ATP-5 population. At minimum, the imputation model will utilize available information collected at baseline and any completed study visits. Further details of the imputation model will be described in the SAP. The Mann-Whitney U statistic will be combined across the imputed datasets to give the test statistic and Rubin's Rules used to define distribution of the test statistic under the null hypothesis. A point estimate of the estimand will be computed by dividing combined test statistic by the number of pairwise comparisons and a 95% confidence interval of the estimand will be computed by inverting the described test of the null hypothesis.

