10. Using the ATP-5 analysis population, forest plots of 95% confidence intervals for the difference in proportions of subjects with each solicited event (a component of DOOR) collected through Visit 3, for each severity threshold (mild or greater, moderate or greater, or severe) will be generated. Tests for differences in proportions between treatment arms will be given by Fisher's exact tests.
11. Using the ATP-5 analysis population, a forest plot of 95% confidence intervals for the difference in proportions of subjects with one or more visits to an ED, one or more visits to an outpatient clinic, or one or more visits to an urgent care center or one or more hospitalizations for persistent or worsening LRTI at any time after randomization (a component of clinical improvement and DOOR) will be generated. Tests for differences in proportions between treatment arms will be given by Fisher's exact tests.
12. Using the ATP-5 analysis population, for each qualifying vital sign (temperature, pulse, respiratory rate, or pulse oximetry) and symptom (cough, sputum production, chest pain, or difficulty breathing), improvement in the sign or symptom at Visit 3 compared to baseline in subjects with the symptom or vital sign abnormality at baseline (a component of clinical improvement and DOOR) will be analyzed. A forest plot of 95% confidence intervals for the difference in proportions of subjects with improvement in the symptom or sign will be generated. Tests for differences in proportions between treatment arms will be given by Fisher's exact tests.
13. Using the ATP-5 analysis population, for each qualifying symptom (cough, sputum production, chest pain, or difficulty breathing), deterioration in the symptom at Visit 3 compared to baseline (a component of clinical improvement and DOOR) will be analyzed in subjects having the symptom at baseline. A forest plot of 95% confidence intervals for the difference in proportions of subjects with deterioration in the symptom will be generated. Tests for differences in proportions between treatment arms will be given by Fisher's exact tests.

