5. Using the ATP-11 analysis population, a forest plot of 95% confidence intervals for the difference in proportions of subjects with one or more visits to an ED, one or more visits to an outpatient clinic, or one or more visits to an urgent care center or one or more hospitalizations for persistent or worsening LRTI at any time after randomization (a component of clinical improvement and DOOR) will be generated. Tests for differences in proportions between treatment arms will be given by Fisher's exact tests.
6. Using the ATP-11 analysis population, for each qualifying symptom (cough, sputum production, chest pain, or difficulty breathing) and for fever, improvement in the symptom or fever at Visit 4 compared to baseline in subjects with the symptom or fever will be

analyzed. A forest plot of 95% confidence intervals for the difference in proportions of subjects with improvement in the symptom or fever will be generated. Tests for differences in proportions between treatment arms will be given by Fisher's exact tests.

7. Using the ATP-11 analysis population, for each qualifying symptom (cough, sputum production, chest pain, or difficulty breathing), deterioration in the symptom at Visit 4 compared to baseline will be analyzed in subjects having the symptom at baseline. A forest plot of 95% confidence intervals for the difference in proportions of subjects with deterioration in the symptom will be generated. Tests for differences in proportions between treatment arms will be given by Fisher's exact tests.
8. Using the ATP11 analysis population, the proportion of subjects with fever in the 24 hours preceding or at Visit 4 (fever is defined as  $\geq 37.8$  °C or 100.0 °F, measured anywhere on the body), unless related to a new process that is unrelated to the prior diagnosis of LRTI will be analyzed. A forest plot of 95% confidence intervals for the difference in proportions of subjects with fever in the 24 hours preceding or at Visit 4 will be generated. Tests for differences in proportions between treatment arms will be given by Fisher's exact tests.

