6.3. Analysis Populations

The primary analysis will be done using the intention-to-treat (ITT) cohort. Other analyses may use according-to-protocol (ATP) cohorts. Analyses of the ITT cohort will include imputation for missing clinical improvement and DOOR.

Reasons for exclusion from each analysis population are summarized in [Table 9](#) and shown by subject in [Listing 5](#). Excluded subjects might satisfy multiple criteria justifying their exclusion but will have only one reason indicated in [Table 9](#) and [Listing 5](#). The exclusion reason indicated will be determined by first exclusion reason met based on the following rules in the order they are listed for each analysis population.

Safety Population Exclusions:

- Subject not treated with any dose of study product

ITT Population Exclusions:

- Non-randomized subjects

ATP Population Exclusions:

- Subject was excluded from ITT
- Subject had major protocol deviation related to I/E criteria
- Did not consume 5 doses of study product by D5V
- First dose of study product not taken within 24 hours of randomization
- Dosing not resumed within 24 h of a missed dose

ATP-5 Population Exclusions:

- Subject was excluded from ATP population
- Subject did not complete D5V
- D5V occurred out of the protocol defined window of Day 5 + 3 days
- D5V was not completed in person
- Data collected is insufficient to define clinical improvement at D5V

ATP-11 Population Exclusions:

- Subject was excluded from ATP population
- Subject did not complete D11V
- D11V occurred out of the protocol defined window of Day 11 + 3 days
- Data collected is insufficient to define clinical improvement at D11V

ATP-28 Population Exclusions:

- Subject was excluded from ATP population
- Subject did not complete D28V
- D28V occurred out of the protocol defined window of Day 28 ± 2 days
- Data collected is insufficient to define clinical improvement at D28V

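### Return visits, ED visits and hospitalisations are compared between arms only in ATP populations, which a subject rescued and stopped before dose 5 leaves because of the event; an as-randomised comparison should be added

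*Protocol*

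**What the plan says.** **Populations.** Protocol 11.4.2 item 6 sets the pattern: "Using the ATP-11 and ATP-28 analysis populations, respectively, the proportion of subjects with one or more emergency department visits for persistent or worsening LRTI" is compared by odds ratio and Fisher's exact test. Item 5 does the same for return visits to an office or urgent care. Item 7, on hospitalisations, begins "Using the subsets of the ATP-11 and ATP-28 analysis populations, respectively, consisting of subjects not hospitalized at the enrollment and randomization visit". Item 11 plans, in ATP-5, "a forest plot of 95% confidence intervals for the difference in proportions of subjects with one or more visits to an ED" or to other settings, and 11.4.3 item 5 repeats this at Day 11: "Using the ATP-11 analysis population, a forest plot of 95% confidence intervals for the difference in proportions of subjects with one or more visits". SAP 8.2.6, 8.2.10 and 8.3.5 follow suit (Tables 32-34, 43 and 44).

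**Entry to those populations.** Protocol 11.4 defines ATP as "subjects with no major protocol deviations regarding inclusion/exclusion criteria that consumed 5 doses of study product by Visit 3". ATP-5, ATP-11 and ATP-28 add conditions on the relevant visit. SAP 6.3 lists "Did not consume 5 doses of study product by D5V" among the ATP exclusions, and all three sets inherit it.

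**The event and its consequence.** In Protocol 3.2.1, criterion 4, "persistent or worsening LRTI is defined as receipt of a non-study antibiotic [parenteral or oral] treatment for LRTI or its complication". Protocol 9.5.2 says "Study product administration may be discontinued if any of the following criteria are met", and one criterion is an inadequate response needing off-study antimicrobial therapy. Protocol 5.4.3 and 6.3 state stopping as mandatory when a halting criterion is met, whereas 9.5.2 states it as permitted. These sections must be reconciled. Sections 5.4.3 and 9.5.2 agree that a subject who stops product is not thereby withdrawn from the study.

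**The concern.** These tables are where a reader would look to see whether withholding an antibiotic leads to more unscheduled care. A subject who seeks care on Day 3, receives an antibiotic for LRTI and stops study product has had the event. That subject has also taken fewer than five doses, and so leaves both the numerator and the denominator. The analysis set is then partly defined by the outcome.

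Taken alone, this lowers the event proportion in any arm where it happens. If it happens sufficiently more often on placebo, the placebo-minus-azithromycin difference is understated, and the table could reassure when it should not.

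**Working it through.** **Step 1: the plan's own figure.** From Protocol 11.2 and SAP 6.6, 560 / (1 - 0.169) = 673.9, which is the stated 674. The planned gap between ITT and ATP-5 is 674 - 560 = 114 subjects (16.9%). That gap covers every reason for exclusion, so it is not a count of rescues.

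**Step 2: model.** The documents give no event rates, so every rate below is an assumption. For one arm, let e be the probability of early rescue, l the probability of a later event in those not rescued early, and f the share of early-rescued subjects who stop before dose 5. If only those subjects are removed:

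- ITT rate = e + (1 - e)l
- ATP rate = [e(1 - f) + (1 - e)l] / (1 - ef)

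**Step 3: early rescue commoner on placebo.** Take e = 3% on azithromycin and 8% on placebo, l = 5% in both, and the same f in both arms.

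- ITT: 0.03 + 0.97 × 0.05 = 7.85%, against 0.08 + 0.92 × 0.05 = 12.60%. The difference is 4.75 points and the odds ratio 1.69.
- ATP at f = 50%: (0.015 + 0.0485)/0.985 = 6.45%, against (0.04 + 0.046)/0.96 = 8.96%. The difference is 2.51 points.

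| f | azithromycin | placebo | difference | odds ratio |
|---|---|---|---|---|
| 25% | 7.15% | 10.82% | 3.66 | 1.57 |
| 50% | 6.45% | 8.96% | 2.51 | 1.43 |
| 75% | 5.73% | 7.02% | 1.29 | 1.24 |

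With no later events (l = 0), which is close to the Day 5 tables, 5.00 points becomes 3.86, 2.64 or 1.36, and the odds ratio stays at 2.81.

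**Step 4: equal early rescue.** Take e = 4% in both arms and l = 5% against 10%. ITT gives 8.80% against 13.60%, a difference of 4.80 points.

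- Same f in both arms: 4.85, 4.90 or 4.95 points, so no shrinkage. The odds ratio rises from 1.63 to 1.71, 1.80 or 1.93.
- f = 25% on azithromycin and 75% on placebo: 7.88% against 10.93%, a difference of 3.05 points.
- f = 75% on azithromycin and 25% on placebo: 5.98% against 12.73%, a difference of 6.75 points.

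**Step 5: a small excess of early rescue on placebo need not shrink the difference.** With e = 5% against 5.5% and l = 5% against 20%, the ITT difference is 14.65 points and the ATP differences are 14.74, 14.83 and 14.91.

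**Step 6: other exclusions.** Repeat Step 3 at f = 25%, also removing an assumed 15% of event-free subjects for non-adherence or visit problems.

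- Azithromycin: 0.071 / (0.071 + 0.97 × 0.95 × 0.85) = 8.31%, above its ITT rate of 7.85%.
- Placebo: 0.106 / (0.106 + 0.92 × 0.95 × 0.85) = 12.49%.
- The difference is 4.18 points. The shrinkage is 12%, against 23% in Step 3.

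**The case against.** **Existing ITT information.** An LRTI visit with an antibiotic fails criterion 4 of clinical improvement, which is compared in ITT at Days 5, 11 and 28. It also enters DOOR. SAP Table 49 gives ordinal categories 6 and 7 by arm in ITT at all three visits, with Wilson intervals. Table 9 shows exclusions by arm, and Listings 2, 19 and 20 show reasons for stopping and individual events. This stands, and a crude subtraction from Table 49 is possible. But categories 6 and 7 are not restricted to LRTI visits (SAP 6.5.4), category 6 merges ED, outpatient and urgent-care visits, and no between-arm estimate is planned. The composites do not isolate these events.

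**Weight.** SAP 8.1.1 makes every non-primary analysis supportive, and the trial is powered only for clinical improvement. This also stands. It argues for adding a comparison beside the planned tables, not for displacing them.

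**Direction.** A reader might infer that the ATP tables must understate harm on placebo whenever early rescue is commoner there. Step 5 is a counter-example, Step 4 shows dependence on how stopping is shared between arms, and Step 6 shows other exclusions offsetting the effect. A reader might also take the 16.9% loss as rescued subjects because Protocol 11.2 names rescue medication as a cause. SAP 6.6 defines the loss more broadly. Nor does every rescued subject leave: one who still takes five doses, or is rescued after the fifth, is not excluded on dosing grounds.

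**Conclusion.** The point holds as a gap in the planned analyses. Visits and hospitalisations as separate outcomes have no as-randomised comparison, and the populations used can lose a subject because of the event counted. This follows from the documents under either reading of the stopping rule; the reading affects only how often it happens.

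The effect on the arm difference cannot be sized or signed from the documents. It shrinks the difference when early rescue with stopping is sufficiently more common on placebo, and otherwise can leave it unchanged or raise it. The figures under working are examples on assumed rates, not bounds. Apart from Step 6 they remove rescued subjects only, and apart from the last two lines of Step 4 they use the same f in both arms.

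A reader might carry this over to the non-inferiority conclusion. That would be wrong: the primary analysis is ITT, and the choice of population for these separate tables does not alter it. The change should be made, but the trial's main result does not depend on it.

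**What to change.** Add ITT versions of Tables 32-34, 43 and 44 by randomised arm, shown beside the planned ATP tables. Give the risk difference with Miettinen-Nurminen interval, the odds ratio and Fisher's test. For hospitalisations, keep the restriction to subjects not hospitalised at enrollment.

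- Count any recorded event within the window, whether or not the visit was completed or in window.
- Where the visit was missed or out of window, count through the planned study day, which SAP 3.3.1 already uses for ITT. Treat status as known if a later completed contact covers the period.
- Leave subjects with no recorded event and no covering contact as missing, consistent with SAP 6.5.1.4 and 6.5.2.3. Report their number by arm and analyse those with known status.
- Give two sensitivity results: missing set to no event; and missing set to event on placebo and no event on azithromycin.
- If multiple imputation is used, take all ITT subjects with observed status as donors, not only ATP-5 as in SAP 8.4.1, and pool the risk difference by Rubin's rules.

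Optionally, repeat the antibiotic-days comparison (11.4.2 item 4) in ITT subjects with non-missing days under SAP 6.5.5. Separately, reconcile Protocol 5.4.3, 6.3 and 9.5.2 on stopping product.

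The cost is a few tables. No new data are needed, because subjects who stop product are asked to stay in follow-up and medically attended visits are sought at Visits 3 to 5. The downside is dependence on missing follow-up. With 337 per arm, each placebo subject of unknown status moves the worst-case bound by about 1/337 = 0.30 points, so 10 move it by about 3.0 and 20 by about 5.9. The bound is informative only if few are missing.

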### **11.4.3 Exploratory Analyses**

1. Using the ATP-5 analysis population, mean changes in PCT levels at Visit 3 relative to baseline will be computed for placebo versus azithromycin, in addition to an estimated difference in mean PCT changes and associated 95% confidence intervals. Significance of a difference in mean PCT changes between treatment groups will be tested by a Wilcoxon test. Details of the analysis will be described in the SAP.
2. Using the ATP-5 analysis population, logistic regression will be used to test whether changes in PCT levels at Visit 3 relative to baseline are associated with clinical improvement at Visit 3, after accounting for treatment assignment.
3. The Day 11 DOORs (an ordinal outcome defined in Section 3.2.3) will be compared between the placebo and azithromycin arms. The sum of the probability that a randomly selected subject will have a better DOOR if assigned to the placebo arm plus one-half the probability of equal DOORs will be estimated. The null hypothesis to be tested is that the probability is equal to 0.50 (lack of superiority of azithromycin therapy). The analysis will be carried out using the ITT analysis population, with missing DOOR values (treated as continuous) imputed using multiple imputation, utilizing linear regression models. The analysis will be repeated using the ATP-11 population. At minimum, the imputation model will utilize available information collected at baseline and any completed study visits. Further details of the imputation model will be described in the SAP. The Mann-Whitney U statistic will be combined across the imputed datasets to give the test statistic and Rubin's Rules used to define distribution of the test statistic under the null hypothesis. A point estimate of the estimand will be computed by dividing combined test statistic by the number of pairwise comparisons and a 95% confidence interval of the estimand will be computed by inverting the described test of the null hypothesis.
4. Using the ATP-11 analysis population, forest plots of 95% confidence intervals for the difference in proportions of subjects with each solicited event (a component of DOOR) collected through Visit 4, for each severity threshold (mild or greater, moderate or greater, or severe) will be generated. Tests for differences in proportions between treatment arms will be given by Fisher's exact tests.

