6.3.3. Safety Population

The Safety analysis population will consist of all subjects with recorded receipt of any amount of study product. The analyses on the Safety analysis population will be performed per treatment actually received.

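### The Day 5 solicited-event comparison is run only in subjects who took all five doses, so it can miss events that stopped treatment; the Safety population should carry it.

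*Protocol*

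**What the plan says.** Secondary objective 9 compares solicited events by Day 5, and exploratory objective 3 does so by Day 11. Protocol 11.4.2 item 10 sets the Day 5 analysis: "Using the ATP-5 analysis population, forest plots of 95% confidence intervals for the difference in proportions of subjects with each solicited event". Protocol 11.4.3 item 4 sets the Day 11 analysis: "Using the ATP-11 analysis population, forest plots of 95% confidence intervals for the difference in proportions of subjects with each solicited event". Both use three severity thresholds and Fisher's exact tests. SAP 8.2.9 and 8.3.4 keep these populations and add Miettinen-Nurminen intervals (Tables 56-61, Figures 2-7).

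Protocol 11.4 limits the ATP populations to subjects "that consumed 5 doses of study product by Visit 3". SAP 6.3 gives the matching exclusion: "Did not consume 5 doses of study product by D5V". The footnotes to Tables 56-61 narrow the denominator again, to subjects whose event records are complete over the window.

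Protocol 9.5.2 allows study product to be discontinued when "Any clinical adverse event (AE), intercurrent illness, or other medical condition occurs" and, in the investigator's opinion, continuing is not in the subject's interest. It adds: "Subjects may stop study drug treatment at any time of their own volition or at the advice of their treating provider". Those who stop remain under follow-up: "Subjects who stop study product for any reason will be regarded as having withdrawn from treatment but not as having withdrawn from the study".

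The Protocol defines no safety population. SAP 6.3.3 does: "The Safety analysis population will consist of all subjects with recorded receipt of any amount of study product".

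**The concern.** Under these rules, exclusion from the analysis can be caused by the outcome being compared. Someone who stops on Day 2 or 3 because of diarrhea or a rash has fewer than five doses, falls outside ATP, and so falls outside ATP-5. Treatment-limiting events are the ones most exposed, so the moderate-or-worse and severe thresholds have most to lose.

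This matters more here than in most trials. Protocol 9.1 collects no azithromycin-related adverse events or serious adverse events apart from the solicited ones, so these five events are the trial's structured evidence on drug harm. Protocol 2.3.2 counts fewer antibiotic-related adverse events among the benefits of withholding treatment. The primary non-inferiority conclusion is not affected.

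**Working it through.** **1. The plan's own shrinkage from randomized to ATP-5.** SAP 5 gives 674 randomized, 16.9% loss and 560 in ATP-5. Check: 560 / (1 - 0.169) = 674, which reproduces. So 674 - 560 = 114 subjects, about 57 per arm, are expected outside ATP-5. The SAP describes this loss as follow-up or rescue medication. It does not say how many, if any, stop for an adverse event.

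**2. Which analyses cover all treated subjects.**

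| Source | Population | Window | Between-arm test |
|---|---|---|---|
| SAP 8.2.9, Tables 56-58 | ATP-5, full records only | Day 1 to Day 5 visit | Yes |
| SAP 8.3.4, Tables 59-61 | ATP-11, full records only | Days 1-11 | Yes |
| SAP 9.3.1, Table 69 | Safety, with any solicited data | Whole follow-up (captured Days 1-11) | Yes |
| Tables 67-68 | Safety | Each day, and any post dose | No |
| DOOR, SAP 8.2.8 | ITT, imputed | Day 1 to Day 5 visit | On the composite only |

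Table 69 uses the same five events, the same thresholds, Miettinen-Nurminen intervals and Fisher tests. Because solicited events are captured only through Day 11, it is in substance a Day 11 test in all treated subjects. No row gives a between-arm test of solicited events through the Day 5 visit in all treated subjects. DOOR does not fill that gap: under SAP 6.5.4 event severity separates ranks 1 to 4 only, that is, among subjects with clinical improvement.

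**3. Illustration of the possible size.** The documents state no event or stopping rates, so every rate here is assumed. Let p be the event risk in an arm and s the share of event subjects who stop early because of the event. If exclusions for other reasons are unrelated to the event, the risk seen in ATP is p(1 - s) / [p(1 - s) + 1 - p].

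For 20% azithromycin and 10% placebo with s = 25% in both arms: 0.150/0.950 = 0.158 and 0.075/0.975 = 0.077, a difference of 8.1 points where all treated subjects would show 10.0.

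| Event rates | All-treated difference | s = 10% | s = 25% | s = 50% |
|---|---|---|---|---|
| 10% vs 5% | 5.0 | 4.6 | 3.9 | 2.7 |
| 20% vs 10% | 10.0 | 9.3 | 8.1 | 5.8 |
| 30% vs 20% | 10.0 | 9.5 | 8.5 | 6.5 |
| 3% vs 1% (severe) | 2.0 | - | 1.5 | 1.0 |

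Unequal stopping, at 20% vs 10%: with 25% of azithromycin and 10% of placebo event subjects stopping, the ATP difference is 6.7. With the shares reversed it is 10.7, an overstatement. With no event-driven stopping it stays at 10.0.

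**The case against.** A reader might infer that subjects who stop azithromycin are removed from every comparison of harm, and that the drug's harm is therefore understated. The documents support neither step.

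On the first, Table 69 includes anyone who took any study product and has solicited data. Stoppers stay in follow-up and can be counted there. Tables 67-68 add daily counts in the same population. The ATP displays also have a stated purpose: item 10 presents solicited events as a component of DOOR, and the neighboring items break down the composite in the same ATP-5 population. SAP Section 9 holds the safety comparison, and SAP 8.1.1 treats every analysis other than the primary as supportive. All of this stands, and it largely answers the point for Day 11. It leaves Day 5 without an all-treated test.

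On the second, attenuation needs event-driven stopping, for which no rate is given. The trial is double-blind, so higher stopping on azithromycin cannot be taken for granted. A missed dose followed by resumption within 24 hours does not exclude a subject. An event that begins after the fifth dose cannot cause exclusion for missed doses, which protects most of the Day 11 window but much less of the Day 5 one. If the bias is toward zero, it also works against the case for withholding antibiotics, not for it. These points limit the size and certainty of the problem. They do not make a five-dose population a sound choice for comparing harm.

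**Conclusion.** The point holds for Day 5. The only between-arm test of solicited events through that visit conditions on completing treatment, which the event itself can prevent. Bias toward zero is the likely direction, not an established fact: none without event-driven stopping, and reversed if placebo event subjects stop more often. In the equal-stopping illustrations the difference shrinks by about 5% (30% vs 20%, s = 10%) to about 49% (severe 3% vs 1%, s = 50%). All of those rates are assumed.

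For Day 11 the remaining issue is one of assignment. The all-treated test exists, but the objective is answered by the ATP-11 tables. The matter concerns a secondary and an exploratory objective, and it should be corrected because the better population is already defined and programmed.

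**What to change.** - Add a through-Day-5-visit comparison in the Safety population, with the same events, thresholds, Miettinen-Nurminen intervals and Fisher tests as SAP 8.2.9.
- Name that table as the main answer to secondary objective 9, and Table 69 as the main answer to exploratory objective 3. Keep Tables 56-61 and Figures 2-7 as supportive.
- Do not carry the complete-record restriction into the Safety version, or early stoppers with diary gaps would be lost again. Count any observed event at or above the threshold, as SAP 6.5.3 already does for grade 3. Report denominators and the number of subjects with gaps by arm.
- Reconcile SAP 6.3.3, which analyzes safety by the treatment actually received, with the opening of SAP 9, which uses the randomized assignment.
- Correct the citation in SAP 9.3.1: it points to Table 68 for the dichotomized comparison, but that shell is Table 69, and Table 68 is the placebo by-day table.

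The cost is one added table, a population flag, a denominator rule and some wording, with no new data. The downside is that some treated subjects have incomplete diaries, so events falling in the gaps will be missed; the reported gap counts let a reader judge how much.
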